## STUDY PROTOCOL

The aim of this study is to test in vivo a new technique to evaluate the kinematics of the patello-femoral joint in patients undergoing total knee replacement. In particular, this study is divided into two steps. In the first step, the acquisition of knee kinematics is acquired intra-operatively. This will allow the surgeon to have a more complete comprehension of the knee functioning. Moreover, since the prosthetic implantation can potentially alter the functioning of both tibio-femoral joint and patello-femoral joint, it is necessary, in a second step, to perform knee kinematic evaluations at 6-months follow-up on the same patients. In this way it will be possible to evaluate the biomechanical behavior of the replaced knee joint and to observe anomalies / differences with respect to both normal and pre-implantation joint. In the second phase, the acquisitions will be performed using videofluoroscopic and roentgen-stereophotogrammetric techniques. Moreover, always in the second phase, the clinical evaluation of enrolled patients allow to identify the specific advantages and potential complications associated with the prosthesis implantation .

This study involves the recruitment of 20 patients selected for total knee replacement. The specific inclusion and exclusion criteria that can allow an adequate intra- and post-operative functional evaluation are reported in the main document.

During the surgery, the alignment of the prosthetic components will be performed with the aid of a standard surgical navigation system (Stryker® - Leibinger, Freiburg-im-Breisgau, Germany) in addition to standard navigation-based procedure for femur and tibia prosthesis component positioning. Particularly, the intra-operative acquisitions of the tibio-femoral and patello-femoral morphology and kinematics will be performed by means a navigation system equipped with an additional innovative device for patellar-based data acquisitions. In addition to standard navigation steps, originally the surgeon will now collect the patellar medial, lateral and distal prominences, along with the anterior and the posterior aspect; this will allow to assess exactly the real patellar thickness and to set via computer-assistance the more proper position of the patellar cutting jig; once the patellar cut is executed, the surgeon can select the best location for positioning the patella polyethylene component using navigation-based data, in addition to usual visual inspection and standard, i.e. not computer-assisted, procedures. Six months after the surgery, 3D vidoe-fluoroscopic analysis and gait analysis combined with electromyography will be performed on the same patients to evaluate in vivo replaced knee kinematics and kinetics during the execution of a number of motor tasks of daily living; clinical scoring will be performed at 6, 12 and 24 months follow-ups.

## STATISTICAL PLAN

The population size was estimated by considering previously reported data obtained using the same acquisition technique of the present study [1,2], and by meeting the criteria for achieving differences in measurements with 80 % statistical power and an  $\alpha$ -level of 0.05. The differences in patellar implantation parameters and kinematic variables and before and after total knee replacement treatment were tested for significance using the paired t-test and one-way analysis of variance. P values were considered significant for  $p < 0.05$ .

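### In the supplied text, p < 0.05 is applied to each of several variables with no primary variable, multiplicity control or exploratory label, so 0.05 holds per test and not for the set

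*Combined protocol and SAP*

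**What the plan says.** The analysis rule is two sentences in the Statistical Plan. The first covers what is compared: "The differences in patellar implantation parameters and kinematic variables and before and after total knee replacement treatment were tested for significance". The methods it names are a paired t-test and a one-way ANOVA. The second sets a threshold of p < 0.05 for all results alike; it opens with "P values were considered significant for" and gives that one value.

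The sample-size sentence in the same section says the number of patients was set "by meeting the criteria for achieving differences in measurements with 80 % statistical power", with alpha at 0.05. It does not say which measurement. The Study Protocol section gives the number: "This study involves the recruitment of 20 patients selected for total knee replacement". It states the aim as "to test in vivo a new technique to evaluate the kinematics of the patello-femoral joint".

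The supplied text contains no primary variable, no order of testing, no adjustment, no post hoc procedure, and no exploratory or pilot label. The Study Protocol section mentions a main document, which was not supplied, and cites it only for the eligibility criteria.

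**The concern.** A single 0.05 threshold controls the error of one test. Here it is applied to at least two kinds of measurement, each in the plural, and any result below it counts as significant. The chance that at least one unchanged variable crosses the line is then above 5%, and it grows with the number of unchanged variables.

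A published result will name its variable, so a reader will know which one was significant. The reader will not know whether that variable was the one the study set out to test or was picked from the set after the results were seen. The same gap leaves the 80% power statement without a variable to refer to.

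**Working it through.** **Inputs from the documents.** 20 patients in one group, compared before and after (Study Protocol). Alpha 0.05, power 80%, threshold p < 0.05, paired t-test and one-way ANOVA (Statistical Plan).

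**Not given, so assumed.** Two-sided tests; the number k of tested variables that are truly unchanged; the correlation between their paired differences.

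**Step 1: the plan's own figure.** The 20 patients cannot be re-derived, because no variable, effect size or standard deviation is stated. Working backwards with a two-sided paired t-test (19 degrees of freedom, noncentral t), 20 pairs give 80% power for a mean change of 0.66 SD of the paired differences. The noncentrality is 0.66 × √20 = 2.95. This is what the sample can detect for one variable tested once at 0.05. It does not show the power statement to be wrong.

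**Step 2: chance of at least one false positive.** For k independent unchanged variables the chance is 1 − 0.95^k:
- k = 2: 1 − 0.9025 = 0.0975
- k = 3: 1 − 0.8574 = 0.1426
- k = 4: 1 − 0.8145 = 0.1855

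For correlated variables it was simulated: paired t-tests, n = 20, equally correlated normal differences, no true change in the k variables.

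| Truly unchanged variables | Corr. 0 (exact) | Corr. 0.5 | Corr. 0.8 | Corr. 0.95 |
|---|---|---|---|---|
| 2 | 9.8% | 9.1% | 7.9% | 6.5% |
| 3 | 14.3% | 12.8% | 10.0% | 7.5% |
| 4 | 18.5% | 15.8% | 11.6% | 8.2% |

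Repeat runs differ by a few tenths of a percentage point. Every cell is above 5%. The expected number of false positives is 0.05 × k whatever the correlation: 0.10, 0.15 and 0.20.

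**Step 3: what ANOVA contributes.** The plan does not say which comparison the one-way ANOVA serves. If it comes before pairwise tests, it can limit error among the levels of one variable. In an illustration with one variable, three uncorrelated levels and no true differences, requiring a significant ANOVA first cut the error from 12.5% to 5.0%. It does nothing across different variables.

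**Step 4: what the remedies do to power.** For a true change of 0.66 SD with 20 pairs:
- One named primary at 0.05: power 80%, false-positive chance for that claim 5%.
- Bonferroni over four variables, 0.05 / 4 = 0.0125 each: power 58%.

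Naming one primary therefore keeps the planned power; adjusting across the whole set would not.

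**The case against.** The strongest case on the other side is that this is a 20-patient, single-group study of a measurement technique. Its second step is largely descriptive, and strict control of error over all variables is partly a convention in such work. That stands as an argument against requiring adjustment. It does not answer the omission: the plan uses power, alpha and a significance threshold, and should either say what these cover or call the tests exploratory.

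Some stronger readings are tempting but are not supported.

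- **That two plurals mean at least four tests, hence an error of at least 12–19%.** Those rates need four unchanged variables and correlations no higher than 0.8. The protocol itself expects that implantation may alter both joints, and a variable that truly changes cannot give a false positive. Four unchanged variables is not a floor.
- **That the ANOVA must add further error.** Its role is not stated. It may replace or precede t-tests rather than add to them.
- **That the study has no primary variable anywhere.** The main document was not supplied. That it is cited for eligibility does not show that it lacks endpoints.
- **That the aim dictates the primary variable.** The aim is to test a technique. It makes a patello-femoral kinematic variable a natural choice, but the documents do not prescribe one.

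The sentence on what is compared is also garbled. It is unclear whether the implantation parameters have a before value at all, so treating every variable as a paired difference is a modelling assumption. These variables would still be judged at 0.05.

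Finally, the Statistical Plan is written in the past tense, so analysis may already have taken place. That affects which remedy applies, not whether one is needed.

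**Conclusion.** The concern holds, limited to the supplied text. The 0.05 level applies per test and not to the set, and the plan gives a reader no way to tell a pre-specified finding from a selected one.

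The inflation is a range: about 6–10% with two truly unchanged variables, 7–14% with three and 8–19% with four. It rests on two-sided paired tests in 20 patients and equal correlations between 0.95 and 0. None of the counts or correlations comes from the documents. The direction does not depend on them in any case tried: with two or more unchanged variables the rate exceeded 5%.

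This should be corrected, but it does not make the data unusable, and it does not show the stated 80% power to be false.

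**What to change.** Before the data are analysed, amend the Statistical Plan as follows.

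1. Name one primary before/after contrast: the variable, and which after measurement is meant. A patello-femoral kinematic variable is preferable, since the Study Protocol section centres the study on these. Test it at two-sided 0.05.
2. Tie the 80% power statement to that variable.
3. Say which comparison the one-way ANOVA serves. Report it and all other comparisons with estimates and confidence intervals, labelled exploratory, without confirmatory claims of significance.
4. If the data have already been seen, name no primary after the fact; label all tests exploratory.
5. If the main document already names a primary variable, repeat it in the Statistical Plan.

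The cost is wording only, with no extra patients or procedures. The downside is that fewer results can be called significant, and the primary has to be settled in advance.

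### An unqualified one-way ANOVA is named beside the paired t-test for before/after differences in one group of 20 patients; taken literally it ignores the pairing and is conservative

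*Combined protocol and SAP*

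**What the plan says.** The Statistical Plan gives its analysis in one sentence. It lists patellar implantation parameters, then says that "kinematic variables and before and after total knee replacement treatment were tested for significance using the paired t-test and one-way analysis of variance". It does not name the ANOVA's factor or levels, include a patient term, or say which variables go with which test. A surplus conjunction makes the sentence hard to parse, so the ANOVA's role is open.

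The Study Protocol section fixes the design. Twenty patients are recruited, and the second step is "to perform knee kinematic evaluations at 6-months follow-up on the same patients". The first-step measurements come from surgery: "the intra-operative acquisitions of the tibio-femoral and patello-femoral morphology and kinematics will be performed by means a navigation system". For the second step, "the acquisitions will be performed using videofluoroscopic and roentgen-stereophotogrammetric techniques". The stated aim is to look for anomalies or "differences with respect to both normal and pre-implantation joint"; where the normal data come from is not said. The 6-month measurements are taken "during the execution of a number of motor tasks of daily living", and "clinical scoring will be performed at 6, 12 and 24 months follow-ups".

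The sample size is justified by reference to earlier data and to "achieving differences in measurements with 80 % statistical power" at an alpha of 0.05. No effect size, SD or within-patient correlation is given, and the power is not tied to either test.

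**The concern.** With the same patients measured before and after, the comparison is within patients. The t-test is explicitly paired; the ANOVA carries no matching qualifier. Without one, a one-way ANOVA ordinarily means the independent-groups test, and with two levels that is the unpaired t-test. Applied to paired data it charges stable differences between patients to the error term.

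The possible uses visible in the text do not clearly call for that test. Motor tasks and the 6, 12 and 24 month scores are repeated within patients, and the scores are not among the variables in the test sentence. A comparison with a normal joint would suit an independent-groups test only if the normal data come from other subjects. The ANOVA may be meant for the implantation parameters alone, but no factor is given for them either.

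At stake is sensitivity. A real change could be significant on the paired test and not on the ANOVA, and no rule says which result stands.

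**Working it through.** **Inputs from the documents.** n = 20, one group; alpha 0.05; power 80%. Two-sided testing is assumed.

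**Inputs not in the documents.** Effect size, SDs and within-patient correlation ρ. Assumed ρ: 0, 0.3, 0.5, 0.7, 0.8. Assumed SDs: equal, or one occasion's twice the other's, because the two occasions use different instruments.

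**The plan's own figure.** Twenty patients for 80% power cannot be reproduced without an effect size and SD. Inverting it with the noncentral t (19 df), a two-sided paired t-test with n = 20 has 80% power at a mean change of 0.66 SD of the differences. The normal approximation, (1.96 + 0.84)/√20, gives 0.63. The value 0.66 is used below.

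**Why the two tests differ.** With mean change d̄, occasion SDs s₁ and s₂, and sample correlation r:

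- paired: t = d̄√n / √(s₁² + s₂² − 2r·s₁s₂), 19 df
- ordinary one-way ANOVA, two levels: √F = |d̄|√n / √(s₁² + s₂²), 38 df

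So the ANOVA statistic is the paired one multiplied by √(1 − 2r·s₁s₂/(s₁² + s₂²)). At r = 0.5 the multiplier is √(1 − 0.5) = 0.71 with equal SDs, and √(1 − 2 × 0.5 × 2/5) = √0.6 = 0.77 with an SD ratio of 2. Positive correlation shrinks the statistic, and unequal SDs soften the shrinkage.

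**Simulation.** Bivariate normal data, 400,000 studies per cell. Paired power is 80% throughout.

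| ρ | ANOVA power, equal SDs | ANOVA type I error, equal SDs | Tests disagree, equal SDs | ANOVA power, SD ratio 2 | ANOVA type I error, SD ratio 2 |
|---|---|---|---|---|---|
| 0 | 82% | 5% | 5% | 82% | 5.2% |
| 0.3 | 70% | 2.1% | 11% | 73% | 2.8% |
| 0.5 | 54% | 0.75% | 26% | 64% | 1.4% |
| 0.7 | 27% | 0.1% | 53% | 48% | 0.55% |
| 0.8 | 10% | 0.01% | 70% | 37% | 0.3% |

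With an SD ratio of 2 the tests disagree in 4% of studies at ρ = 0, 32% at 0.7 and 43% at 0.8. At ρ = 0 the ANOVA is slightly ahead because it has 38 rather than 19 df.

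**If either test may count.** With equal SDs, type I error is about 6% at ρ = 0 and about 5% at the other values.

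**If the ANOVA is repeated-measures.** With two occasions F equals the square of the paired t on 1 and 19 df. The results are identical and power stays at 80%.

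**Three within-patient levels.** With compound symmetry and an effect giving 80% repeated-measures power (2 and 38 df), the ordinary ANOVA (2 and 57 df) has power of about 81%, 65%, 45%, 16% and 4% at the same correlations. The text does not confirm that any listed variable is tested over three levels, so this only shows that the same mechanism carries over.

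**The case against.** The strongest reply is that no wrong analysis has been shown. The plan nowhere calls the ANOVA unpaired or between-groups, and naming a paired t-test in the same sentence suggests that its authors knew the data are paired. The valid test for the two-occasion contrast is already there. Power is lost only if an ordinary ANOVA overrides it, and nothing says that it does. This stands, and it is why the point is conditional.

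The size is also open to challenge. The correlations are assumed. Intra-operative navigation and 6-month imaging during motor tasks differ in instrument and setting, so a high correlation is not assured. With equal SDs, half of the 80% power is lost only above ρ of about 0.61; between 0 and 0.3 the ANOVA still has 70% to 82%. This stands too, so the figures are an illustration and not a forecast.

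Finally, the protocol points to a main document that is not available here. That reference concerns eligibility criteria only. It limits what can be said about the whole plan, but it does not supply the missing specification.

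What survives is that the documents describe no independent groups, yet the named ANOVA, read in its ordinary sense, needs them.

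**Conclusion.** The point holds in a limited form. The plan names an unqualified one-way ANOVA for before/after differences in a single repeatedly measured group. Taken literally, that test discards the pairing and is conservative when the within-patient correlation is positive. The size depends on the assumed correlation and SD ratio: slight or absent near zero correlation, large at 0.7 to 0.8, and smaller throughout if the SDs differ. There is no harm if the ANOVA is repeated-measures or if the paired t-test alone decides.

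A reader might infer three stronger things that the documents do not support:

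- **That the before/after analysis is invalid.** The paired t-test is named and is appropriate.
- **That false positives are materially inflated.** With positive correlation the ANOVA's error rate falls below 5%. Letting either test count raises it to about 6% at most in the cases examined.
- **That the study will lose most of its power.** That needs a high correlation, the independent-groups version of the ANOVA, and a decision to let it prevail. None of these is stated.

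The change is still worth making, because a better-suited method is available at almost no cost.

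**What to change.** State one test per comparison in the Statistical Plan:

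- For each two-occasion within-patient contrast, the paired t-test alone decides.
- For any implantation or kinematic variable with three or more within-patient levels, replace the one-way ANOVA with a repeated-measures ANOVA or a mixed model with a patient random effect. Name the factor and its levels.
- Keep an independent-groups test only for comparison with a separate normal reference sample, if there is one, and state where that sample comes from.

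The cost is one or two sentences and slightly more analysis work. No new data or patients are needed.
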